2.3.6 Pharmacokinetic/pharmacodynamic population

PK/PD population is defined as all treated subjects as long as they had at least one pharmacodynamic assessment time-matched with pharmacokinetic parameters of interest. The specific population will be defined for each PK/PD analysis.

2.4 STATISTICAL METHODS

Continuous data will be summarized using the number of available data, mean, standard deviation, median, minimum and maximum for each treatment group.

Categorical and ordinal data will be summarized using the number and percentage of patients in each treatment group.

Due to early termination of enrollment, the planned sample size will not be achieved, therefore no hypothesis test will be performed on primary endpoint, confidence intervals will be estimated as two-sided and will be used for descriptive purposes only.

In summary tables, treatment arms will be presented as follows:

- SAR439859 400 mg QD (SAR439859 400 mg)
- SAR439859 200 mg QD (SAR439859 200 mg)
- Letrozole 2.5 mg QD (Letrozole 2.5 mg)

Parameters on demographics and baseline characteristics would be provided by treatment arms and overall.

2.4.1 Demographics and baseline characteristics

Parameters described in [Section 2.1.1](#) will be summarized on the ITT population using descriptive statistics. Analyses for the safety population will be included in the appendices if the size of the safety population is different (>10%) from the size of that in the primary analysis population for any treatment group.

The medical and surgical history will be summarized according to the SOC and PT (SOC will be sorted according to the internationally agreed order (see [Appendix G](#)) and PT by overall decreasing frequency).

2.4.2 Prior or concomitant medications

The prior and concomitant medications will be presented for the ITT population. The anti-cancer therapy will be listed separately.

Medications will be summarized according to the WHO-DD dictionary, considering the first digit of the anatomic category (ATC) class and the first 3 digits of the ATC class (therapeutic category). All ATC codes corresponding to a medication will be summarized, and the patients will be counted once in each ATC category (anatomic or therapeutic) linked to the medication. Therefore, the patients may be counted several times for the same medication.

The tables for prior and concomitant medications will be sorted by decreasing frequency of ATC followed by all other therapeutic classes based on the incidence in SAR439859 400 mg QD column. In case of equal frequency regarding ATCs (anatomic or therapeutic categories), alphabetical order will be used.

2.4.3 Anticancer therapies

A listing of prior anti-cancer treatment, including intent, reason of discontinuation, relapse/progression date, best response, regimen/line number, drug name, start and end date/ongoing, will be provided by patient.

A similar listing will be provided for prior radiation therapy, including location, total dose, intent, start and end date/ongoing.

2.4.4 Extent of investigational medicinal product exposure and compliance

The extent of investigational medicinal product (IMP) exposure will be assessed and summarized on the safety population ([Section 2.3.4](#)), by treatment group.

Following information will be summarized:

- Duration of exposure (days) defined as (date of last dose – date of first dose +1).
- Cumulative dose (mg): the cumulative dose is the sum of all doses during the study treatment exposure.
- Actual dose intensity (mg/day):

$$ADI = \frac{\text{Cumulative Dose (mg)}}{\text{Duration of exposure in days}}$$

- Planned dose intensity (mg/day) is the planned dose at Day 1 per protocol:
 - 400 mg/day for the SAR439859 400 mg QD group
 - 200 mg/day for the SAR439859 200 mg QD group
 - 2.5 mg/day for the letrozole 2.5 mg QD group.
- The relative dose intensity (RDI, in %) for SAR439859 or letrozole is defined as:

$$\text{Relative Dose Intensity} = \frac{\text{Actual Dose Intensity}}{\text{Planned Dose Intensity}} \times 100$$

Summary statistics will be provided for cumulative dose, actual dose intensity and relative dose intensity (according to the following categories: 0-80%, 80-100%, >100%).

Dose modifications

- Dose reduction: a dose is deemed to have been reduced if the dose taken by a patient is lower than the dose taken on the previous day or the day before dose(s) omitted.
- Dose omission: one omission corresponds to a dose with a dose equal to 0 mg/day between two non-zero doses. Several consecutive dose omissions will be counted as one episode of omission.

Dose information variables will be summarized descriptively (n, mean, standard deviation, median, minimum and maximum). Analyses will be performed based on the number of patients. The number of patients with at least one SAR439859 or letrozole dose modification with the following details will be provided:

- Number (%) of patients with at least one dose modification (reduction or omission)
- Number (%) of patients with at least one dose reduction

- Number (%) of patients with at least one dose omission
- Number (%) of dose reductions by patient according to the following categories: 0, 1, >1
- Number (%) of dose omissions by patient according to the following categories: 0, 1, >1
- Number (%) of patients with at least 4 consecutive days of dose omission

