6.4 STUDY INTERVENTION COMPLIANCE

A patient diary will be provided to all participants during treatment.

The person responsible for drug dispensing is required to maintain adequate records of the study treatment. These records (eg, product accountability and inventory forms at site level) include the date the study treatment is received from the Sponsor, dispensed to the participant and destroyed or returned to the Sponsor. The packaging batch number on the pack must be recorded on the drug accountability form.

Participant compliance will be assessed at the Day 7 visit via the patient diary and at the Day 14 visit by counting returned capsules/tablets. At the Day 14 visit, the Investigator/Clinical staff will count the number of capsules/tablets, remaining in the returned packs, and fill in the Intervention Log Form and record the dosing information on the appropriate page(s) of the eCRF. The monitor in charge of the study then checks the eCRF data by comparing them with the IMP which he/she has retrieved and intervention log forms.

On Day 1, while the participant is in the clinic, patient diary will be dispensed and the study staff will demonstrate to the participant how to record information in the patient diary. Participants will note every day the hours of amcenestant/letrozole given PO intake. If vomiting occurred after the intake of capsules/tablets, they need to report it in the same diary. In case of an early vomiting event, the administered dose of amcenestant/letrozole given PO should not be repeated, and the participant should be instructed not to make it up the next day and resume the treatment the next day as prescribed. This information should be recorded in the diary. The diary will then be completed by the participant each day for each dose and will be returned to the study personnel on Day 7 and at the end of study treatment. Participants who inadvertently take 1 extra dose during a day must be instructed to skip the next day's dose.

Participants will be requested to return all unused amcenestant/letrozole given PO to the study site at the end of the study treatment for a full compliance assessment. Clinic staff will record the study medication dosing information based on information from the patient diary and the compliance assessment.

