6.6 DOSE MODIFICATION

If a dose of IMP is vomited or omitted, the participant should not take the dose later or 2 doses at the next planned dose, and this information has to be recorded in the patient diary and eCRF.

Investigational medicinal product dose omission is allowed in case of severe toxicity and the reason should be documented in the eCRF. Doses omitted for toxicity are not to be replaced after the 14-day treatment period or compensated at the next planned IMP intake during the 14-day treatment period.

Conditions for dose modifications are aligned in [Table 3](#). Please refer to letrozole label information on additional specific contraindications and events requiring use precaution, and instruction of dose modification.

Table 3 - Dose modification for amcenestant arms and letrozole arm

NCI-CTCAE grade	Dose modifications
Grade 1 or 2	No dose adjustment required except for Grade 2 alanine transferase defined as an AESI *
Grade \geq 3	Amcenestant and letrozole should be definitely discontinued. No reintroduction is allowed.

NCI-CTCAE = National Cancer Institute Common Terminology Criteria for Adverse Events.

* See [Section 8.3](#)

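### SAP 2.4.4 measures a dose reduction against the previous intake, not the arm's assigned dose, so the descriptive dose-reduction rows miscount a return to normal after a double dose and miss under-dosing that is constant from Day 1

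*SAP*

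**What the plan says.** SAP 2.4.4 (Dose modifications) calls a dose reduced "if the dose taken by a patient is lower than the dose taken on the previous day or the day before dose(s) omitted". For omissions, "one omission corresponds to a dose with a dose equal to 0 mg/day between two non-zero doses", and consecutive omitted days form one episode. These rules feed several rows of the exposure table: "Number (%) of patients with at least one dose reduction", the corresponding omission row, the combined row for a reduction or an omission, and the number of each per patient (0, 1, more than 1).

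The same section does state the assigned dose: "Planned dose intensity (mg/day) is the planned dose at Day 1 per protocol", with 400, 200 and 2.5 mg/day listed by arm. It is used only as the denominator of relative dose intensity (RDI), not in the reduction rule.

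Two protocol passages bear on how the rule behaves. On accidental extra intake, Protocol 6.4 states: "Participants who inadvertently take 1 extra dose during a day must be instructed to skip the next day's dose". Table 3 in Protocol 6.6 contains no reduced dose level. For Grade 1 or 2 it reads "No dose adjustment required except for Grade 2 alanine transferase defined as an AESI", and for Grade 3 or higher "Amcenestant and letrozole should be definitely discontinued. No reintroduction is allowed".

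**The concern.** A dose reduction is normally understood as taking less than the assigned dose. The SAP measures something else, namely a fall from the last dose taken. The two differ in two situations. If the last dose was too high, returning to the assigned dose is a fall and is coded as a reduction. If the dose was too low from the start, there is no fall and nothing is coded.

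Because Table 3 has no reduced dose level, most reductions in the database would be intake errors, not planned step-downs. Intake errors are where the rule misclassifies. At stake is the reading of the reduction rows when the two amcenestrant doses and letrozole are set side by side for tolerability and adherence.

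**Working it through.** The plan states no figure to reproduce here, so the check applies the rules as written to 14-day dosing histories.

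Inputs: the reduction and omission rules, planned doses and RDI formula from SAP 2.4.4; the 14-day treatment duration from Protocol 7.1.1; the skip instruction from Protocol 6.4.

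Formulas:
- Reduction: a non-zero dose lower than the most recent non-zero dose. This covers both the previous-day clause and the clause on the day before an omission.
- Omission: a run of zero days with a non-zero dose before and after it.
- Duration = last dose date − first dose date + 1.
- RDI = 100 × (cumulative dose / duration) / planned daily dose.

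Assumption: a day with no intake is not itself a dose taken. If it were, every omission would also be a reduction, and the half-dose patient would still have none.

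Histories in the 400 mg arm:

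| History | SAP reductions | SAP omissions | Non-zero days below 400 mg | Cumulative mg | Duration (days) | RDI |
|---|---|---|---|---|---|---|
| 400 mg throughout | 0 | 0 | 0 | 14 × 400 = 5600 | 14 | 100.0% |
| 800 on D5, 0 on D6, 400 otherwise | 1 | 1 | 0 | 12 × 400 + 800 = 5600 | 14 | 100.0% |
| 800 on D5, 400 otherwise (no skip) | 1 | 0 | 0 | 13 × 400 + 800 = 6000 | 14 | 107.1% |
| 200 on D1–D14 | 0 | 0 | 14 | 14 × 200 = 2800 | 14 | 50.0% |
| 200 on D1–D7, 400 on D8–D14 | 0 | 0 | 7 | 7 × 200 + 7 × 400 = 4200 | 14 | 75.0% |
| 400 on D1–D7, 200 on D8–D14 | 1 | 0 | 7 | 7 × 400 + 7 × 200 = 4200 | 14 | 75.0% |
| 400 on D1–D13, D14 missed | 0 | 0 | 0 | 13 × 400 = 5200 | 13 | 100.0% |
| 400 on D1–D12, 800 on D13, D14 skipped | 0 | 0 | 0 | 12 × 400 + 800 = 5600 | 13 | 107.7% |

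Row 2 is the patient who follows Protocol 6.4. On Day 7 her 400 mg is compared with the 800 mg taken on the day before the omission, so she has one reduction with no day below her assigned dose. Her omission is real and correctly counted.

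Rows 5 and 6 have the same cumulative dose and the same seven days at half dose, but only the patient who starts at full dose is counted.

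For the first six rows, the 200 mg and 2.5 mg arms give the same counts and RDI once the doses are scaled. For letrozole, a half dose means half of one tablet.

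With the assigned dose as reference, rows 2 and 3 would show no reduction, and rows 4, 5 and 6 would each show one or more.

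**The case against.** The strongest reply is that the same section reports most of this by other measures. RDI is measured against the assigned dose and tabulated in categories (0-80%, 80-100%, above 100%). The constant half-dose patient sits at 50%, in the lowest category. The patient who doubles on Day 13 and skips Day 14 sits at 107.7%, in the highest, with a duration of 13 days. That stands: a reader might infer that the exposure analysis as a whole misses sustained under-dosing, and it does not. Only the reduction and modification rows miss it.

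Nor are overdoses hidden. Protocol 8.3 defines an overdose as at least twice the intended dose and has asymptomatic cases reported as adverse events and symptomatic ones as events of special interest. For the patient who skips the next day, the omission row and the combined modification row are correct, and only her reduction is false.

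A reader might also infer that failing to count a missed Day 14 dose is serious because that dose matters most for the Day 15 tumour sample. The documents do not say so. The endpoint is change after a 14-day treatment period, and Protocol 8.6.1 provides for tissue up to 48 hours after the last dose. Day 14 intake is planned on site (Protocol 8), so a miss would be evident. Requiring a later non-zero dose also has a purpose: it separates an omission from the end of treatment. What remains is narrow. A plain missed Day 14 dose in a patient who has not discontinued gives no omission and an RDI of 100%, and only the 13-day duration shows it.

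None of this defends the reduction rule itself. No other passage brings in the assigned dose or excludes an overdose day as the reference.

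**Conclusion.** The reduction rule is wrong as written, and the consequence is minor. It gives a false reduction after an accidental double dose and no reduction for under-dosing present from Day 1. The error lies in the descriptive reduction rows. It reaches the combined modification row for constant under-dosing, and also where an extra dose is not followed by a skipped day.

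It does not reach the primary analysis, which uses the mITT population and takes no input from dose modifications (SAP 2.3.2, 2.4.5.1.1). It does not reach the per-protocol population either, where the IMP exclusion rests on days of treatment received (SAP 2.3.3).

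The effect cannot be sized. The documents give no frequency for such intake errors. It is tempting to use the planned 42 per arm and say that each misclassified patient moves an arm by 1/42 = 2.4 percentage points. However, SAP 2.4 states that enrolment ended early and the planned size will not be reached, and it gives no final number per arm. The histories above show how the rule behaves, not how often it misfires.

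The conclusion rests on a literal reading of SAP 2.4.4. Programming specifications that already use the assigned dose would remove the fault, but the documents show none.

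**What to change.** In SAP 2.4.4, define a dose reduction as a non-zero daily dose below the arm's planned daily dose already listed there (400, 200 or 2.5 mg). State whether consecutive days below it count as one episode, as is done for omissions, so that the 0, 1 and more-than-1 categories are unambiguous. Tabulate days above the planned dose in a separate row.

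Optionally, flag in the exposure table a missed final scheduled dose in a patient who has not discontinued, since at present only the duration of exposure shows it.

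The cost is a few lines of SAP text and a small change to the exposure programming before database lock, using the diary and eCRF dosing data already collected. It changes a derivation only; dosing instructions and patient management are untouched.

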2.4.5 Analyses of efficacy/pharmacodynamics endpoints

2.4.5.1 Analysis of primary endpoint(s)

2.4.5.1.1 Primary analysis

The primary analysis will be performed on the mITT population defined in [Section 2.3.2](#).

Ki67 at baseline ($Ki67_{pre}$), after a 14-day treatment period ($Ki67_{post}$) and the percentage reduction in Ki67 from baseline defined as $100 \times (Ki67_{pre} - Ki67_{post}) / Ki67_{pre}$ will be summarized by treatment groups using descriptive statistics (such as the number of observations, arithmetic mean, geometric mean, median, standard deviation (SD), minimum, and maximum). The geometric mean of percentage reduction in Ki67 will be calculated with 1 minus geometric mean of proportional change, where proportional change is $Ki67_{post} / Ki67_{pre}$.

The percentage reduction in Ki67 from baseline for each patient will be displayed in a waterfall plot. In the waterfall plot, patients with Ki67 level decreased after 14-day treatment will have negative percentage change. The patients will be ordered from highest positive change to smallest negative change.

Assuming Ki67 value follows a log-normal distribution, $\log(Ki67_{post})$ and $\log(Ki67_{pre})$ will be used to denote the logs of the post-treatment and baseline values respectively. 0.1% will be added to untransformed Ki67 with 0 value to avoid the mathematical anomaly that arises because the log of zero is minus infinity. As a consequence of the assumption of a lognormal distribution, the log proportional changes ie, $\log(Ki67_{post}/Ki67_{pre})$ is also normally distributed. The log proportional change will be compared between treatment arms using an analysis of covariance (ANCOVA) model adjusting for the log Ki67 at baseline. Geometric LS-means ratio of proportional change (and associated 95% CI) between treatment arms will be calculated from the estimate (and associated 95% CI) of the difference of least squared (LS)-means of the log-proportional change (and associated 95% CI) from the ANCOVA model and converted by antilog transformations. For each treatment arm, geometric LS-means of the proportional change from baseline (and associated 95% CI) will be obtained from the ANCOVA model after conversion by antilog transformations. Geometric LS-means of percentage reduction in Ki67 (and associated 95% confidence intervals) will be calculated with 1 minus geometric LS-means of proportional change (and associated 95% confidence intervals). Hypothesis test will not be performed due to early enrollment termination.

Details of primary analysis can be found in [Appendix D](#).

Evaluation of inter-reader variability

The reproducibility of Ki67 measurements among readers will be estimated by calculating an intraclass correlation coefficient (ICC). The definition along with the statistical model for ICC estimation are provided in [Table 3](#).

Table 3 - Estimation of ICC during the trial

Notation	Definition	Model	Consistency or absolute agreement
ICC	The inter-reader agreement on log proportional change from baseline in Ki67 measurement after 14-day treatment period.	Mixed-effect model adjusted for baseline covariate, based on single rating	Absolute agreement

Mean estimations along with 95% confidence intervals will be reported for the ICC. Details of ICC estimation can be found in [Appendix E](#).

The ICC estimate will be checked at the following time-points:

- The interim analysis when 20 patients in each arm evaluable for the primary endpoint ([Section 3](#))
- The analysis when at least 75% patients of the study completed treatment and Ki67 value available for analysis.
- The analysis when all of the patients completed treatment and Ki67 value available for analysis.

The ICC has a range of 0-1, with 1 denoting highest agreement. The ICC estimate at each analysis will be reviewed with study team, and in case a high inter-reader variability is suspected (eg, ICC <0.8), team would evaluate the necessity of inviting a third adjudicator to provide a single Ki67 result based on the readings of two assessors.

In any case, the decision as to whether adjudication will take place needs to be finalized before database lock.

2.4.5.1.2 Subgroup analyses

Evaluation of consistency

The consistency of the results from the primary analysis will be evaluated across pre-defined subgroups in patients available in the subgroup of consideration. The subgroups included but not limited are defined in [Table 4](#). Depending upon the study results, additional subgroups may be examined, and subgroups with small sample sizes may be pooled to create a larger meaningful subgroup. For each subgroup, geometric LS-mean of percentage reduction in Ki67 with their associated 95% CIs and geometric LS-mean ratio of proportional change between treatment arms with their associated 95% CIs will be provided for each treatment arm.

Evaluation of interactions

For each pre-defined factor defined in [Table 4](#), log-fold change in Ki67 will be analyzed using linear regression model with terms for the factor, treatment and their interaction, adjusted by log baseline Ki67. The p-value of the test of interaction will be provided.

Other prognostic factors

Since the results from the primary analysis could be impacted by confounding factors, any potential issues will be examined and, if confirmed, exploratory analysis of the primary endpoint will be done accordingly. A multiple linear regression model will be used to identify prognostic factors among the demographic and baseline characteristics factors described in the [Table 4](#) using a stepwise selection procedure with a 15% significance level for removing effects. For significant prognostic factors identified in the multivariate model, the balance between treatment groups will be assessed.

Table 4 - Subgroup analyses

Prognostic factor	Description
Age	<65 years or ≥65 years
Race	Asian or White or Other
Tumor stage	1 or 2 or ≥ 3
Tumor size (greatest dimension)	≥10 mm to < 20mm, ≥ 20mm
Ki67 level at baseline (per central assessment)	<20% or ≥20%
ER H-score at baseline	Low ER+. (H-score 1-100) or moderate ER+ (H-score 101-200) or high ER+ (H-score 201-300).
Progesterone receptor	< 20% vs ≥20%

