1 PROTOCOL SUMMARY

1.1 SYNOPSIS

Protocol title: Phase 2 window study of two dose levels of amcenestant [SAR439859] (SERD) versus letrozole in newly diagnosed pre-operative post-menopausal patients with ER positive, HER2 negative primary breast cancer

Short title: Phase 2 window study of SAR439859 (amcenestant) versus letrozole in post-menopausal patients with ER+, HER2- pre-operative primary breast cancer (AMEERA-4)

Rationale:

Short pre-surgical trials (also known as “window” trials) are non-therapeutic studies in which patients are treated for 2 to 3 weeks immediately after their diagnostic biopsy and before breast surgery (1). Biomarkers of cellular activity (Ki67) and/or drug target modulation are measured in intraoperative biopsies and/or the surgical specimen.

Short-term preoperative ‘window’ studies of 2-3 weeks treatment are a validated strategy to provide rapid and cost-efficient proof-of-concept for novel treatment approaches by assessing the direct effects of the study treatment on the tumor tissue (1, 2). The principle is to have access to tumor tissue before, under and after treatment for pharmacodynamic assessment and correlative studies thus providing critical insight into the optimal patient population, differences in activity between agents, influence of the tumor biology on sensitivity, and molecular mechanisms of response or resistance (1).

Detailed studies in the neoadjuvant setting in prospective randomized clinical trials have demonstrated the utility and validity of changes in Ki67 as a predictor of benefit from treatment and of long-term outcome (3, 4). Although Ki67 measurements in preoperative trials cannot replace the need for adjuvant trials with clinical endpoints, they can be highly instructive in selecting or rejecting candidate approaches for Phase 3 studies and defining the most appropriate patient populations.

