1 OVERVIEW AND INVESTIGATIONAL PLAN

1.1 STUDY DESIGN

This is an international, prospective, open-label, Phase 2 randomized study of 2-week preoperative treatment in ER positive, HER2 negative invasive primary breast cancer.

After a screening phase of up to 14 days, postmenopausal women with early breast cancer will be randomly (1:1:1) assigned to one of the following treatment arms: amcnestrant 400 mg QD, amcnestrant 200 mg QD or letrozole 2.5 mg QD. Patients will be treated for 14 days. The surgery date should be fixed before randomization. The surgery is to be performed 1 (+1) day after the last dose of study treatment.

Approximately 126 patients will be randomized such that 120 evaluable participants are reached. A total of 40 evaluable participants per treatment arm are expected.

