1.3 DETERMINATION OF SAMPLE SIZE

The sample size is determined based on the following assumptions:

- The geometric mean of percentage reduction in Ki67 after a 14-day treatment period for the control arm is assumed to be 70% (1, 2, 3).
- The geometric mean of reduction in Ki67 after a 14-day treatment period is increased to 85% for each SAR439859 arm. Therefore the geometric means of residual Ki67 (defined as one minus the geometric mean of reduction) are assumed to be 30% for the control arm and 15% for treatment arms, corresponding to a log fold difference of -0.693 ($\log(0.15) - \log(0.3)$) under the alternative hypothesis.
- The standard deviation of the log-fold change after a 14-day treatment period is assumed to be 1.

[figure not shown]
A total of 40 evaluable participants (where evaluable are defined as participants who have both baseline and post treatment available biopsies with Ki67 values) per treatment arm will be needed, in order to achieve 85% marginal power at the overall one-sided Type I error rate of 2.5% controlled with an Hochberg procedure, based on a one-sided t-test on the log-transformed data. The disjunctive power, ie, the probability to reject at least one null hypothesis, that the true log-fold change in Ki67 after a 14-day treatment period for both SAR439859 arms and the control arm are the same, is estimated at 91.5%.

Allowing for a 5% non-evaluable participant rate, the total sample size for randomization is 126 participants (42 per treatment arm).

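### Treatment-by-factor interactions are tested only on banded baseline measures; using the measured values is a cheap gain that matters if a modifier is roughly linear and large

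*SAP*

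**What the plan says.** SAP 2.4.5.1.2 fits, for each factor in Table 4, a "linear regression model with terms for the factor, treatment and their interaction, adjusted by log baseline Ki67" to the log-fold change in Ki67, and reports the interaction p-value. Table 4 splits age at 65 years, tumour size at 20 mm, central baseline Ki67 at 20% and PgR at 20%. ER H-score has three bands: "Low ER+. (H-score 1-100) or moderate ER+ (H-score 101-200) or high ER+ (H-score 201-300)". Race and tumour stage are categorical by nature. Small subgroups may be pooled.

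The same section continues: "A multiple linear regression model will be used to identify prognostic factors among the demographic and baseline characteristics factors described in the" Table 4, by stepwise selection. SAP 2.4.5.2 plans a stepwise logistic model for a 50% fall in Ki67 with the same factor list. Neither passage states how the factors are coded.

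The measured values are elsewhere in the plan:
- SAP 2.1.1 lists age and central Ki67 as both quantitative and qualitative variables.
- SAP 2.1.3.2 and 2.4.5.2 analyse the ER H-score as a number.
- Protocol 8.1.2 measures tumour size by ultrasound.
- For PgR, SAP 2.1.1 lists only a status. SAP 2.4.7.2.2 says that it will be analysed like the ER protein, which implies a number but does not specify one.

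No interaction test on a measured scale is planned anywhere.

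**The concern.** Banding a continuous modifier discards the variation within each band. If the treatment effect changes gradually with the factor, a band-by-treatment test has less power than a test on the measured value.

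Baseline Ki67 is the clearest case. SAP 2.4.5.1.1 and Appendix D make log baseline Ki67 the continuous covariate of the primary ANCOVA, and it stays as a main effect in the interaction model. Yet only a 20% indicator of the same variable may interact with treatment.

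The Protocol synopsis describes window studies as giving access to tumour tissue, "thus providing critical insight into the optimal patient population, differences in activity between agents, influence of the tumor biology on sensitivity". Effect modification is part of that aim. SAP 2.4 has dropped the hypothesis test on the primary endpoint after early termination of enrolment, but the interaction p-values remain. What is at stake is the chance of seeing a real modifier in an exploratory analysis.

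**Working it through.** **1. Plan's inputs.** From SAP 1.3: "corresponding to a log fold difference of -0.693" and "The standard deviation of the log-fold change after a 14-day treatment period is assumed to be 1". From SAP 1.1: patients are "randomly (1:1:1) assigned to one of the following treatment arms", with 40 evaluable per arm expected. The plan's figure is "85% marginal power at the overall one-sided Type I error rate of 2.5% controlled with an Hochberg procedure", and 91.5% disjunctive power. Simulating two one-sided t-tests against a shared control (40 per arm, difference 0.693, SD 1, Hochberg at 2.5%) gives 84.8 to 85.0% marginal and 91.6% disjunctive. The primary design reproduces. No power, alpha or effect size is stated for any interaction.

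**2. Assumptions, none from the documents.** Two-sided 5% interaction F test, residual SD 1, and a linear modifier with the same slope b (log units per SD of the factor) in both amcenestrant arms relative to letrozole. Ki67 is log-normal with median 25% and log SD 0.5. Age has mean 65 and SD 9. H-score is skewed high, with 1%, 25% and 74% in the three bands. For scale, b = 0.693 equals the whole planned treatment effect: the benefit vanishes one SD in one direction and doubles one SD in the other.

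**3. Hand check.** With n per arm, the noncentrality for the measured value is about λ = b² / (1/n + 1/(2n)) = (2n/3)b². A split of a normal factor at quantile p (normal point c) keeps the fraction φ(c)² / [p(1−p)]. At the median this is 2/π = 0.637. For n = 40, 2n/3 = 26.67.

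| b | λ measured | Power | λ median split | Power | Loss (points) |
|---|---|---|---|---|---|
| 0.20 | 1.07 | 14% | 0.68 | 10% | 3 |
| 0.35 | 3.27 | 34% | 2.08 | 23% | 11 |
| 0.50 | 6.67 | 62% | 4.24 | 43% | 19 |
| 0.693 | 12.81 | 89% | 8.15 | 71% | 18 |

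Power is noncentral F with 2 and 113 df; losses are from unrounded values. This large-sample form is slightly optimistic for both tests.

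**4. Simulation, 40 per arm** (3,000 runs per cell; b = 0.35 / 0.50 / 0.693).

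| Factor | Measured | Table 4 bands | Loss (points) |
|---|---|---|---|
| Baseline Ki67 | 32 / 60 / 87% | 20 / 37 / 62% | 12 / 23 / 25 |
| ER H-score | 32 / 58 / 86% | 20 / 36 / 62% | 12 / 22 / 24 |
| Age | 31 / 58 / 86% | 22 / 38 / 65% | 9 / 20 / 21 |

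Type I error is near 5% for both tests. A repeat for Ki67 and age with 4,000 runs agrees to within about 2 points. Tumour size and PgR were not simulated.

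**5. Where the figure changes.**
- *Small slope.* At b = 0.20 and 40 per arm, power is about 13 to 14% measured against 9 to 10% banded. Across runs the loss was 1 to 4 points.
- *Fewer patients.* The final number is not given. At an illustrative 20 per arm, Ki67 gives 17 / 33 / 55% against 12 / 21 / 33%, a loss of 5 / 12 / 22 points. The losses at 40 per arm were 12 / 23 / 25.
- *Uneven cuts.* With 25:75 to 10:90 splits or uneven thirds, the loss is about 12 to 53 points when measured-scale power is 30 to 89%.
- *Step at the cut.* For steps of 0.6 to 1.4 log units exactly at a median cut, banding has 25 to 89% power against 17 to 66%. At a 30:70 cut it has 22 to 82% against 14 to 53%. Banding gains 8 to 29 points.
- *Step away from the cut.* With a step at the median and a cut at the 25th percentile, the measured value wins again: 34% against 19% (step 0.9) and 54% against 29% (step 1.2).

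**The case against.** The strongest reply is that these are exploratory subgroup analyses, with no alpha, power or decision rule attached. Matching the interaction test to the bands used for the subgroup display is a common convention. A linear term carries its own assumption, and if the effect really is a step at the cut, banding is the better test. All of that stands. It limits the importance of the point, but gives no reason to prefer the bands: neither document argues for a step at any of the Table 4 cuts.

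Five stronger readings are tempting, and the documents do not support them:
- *That banding costs 10 to 25 points for all five factors.* Only three were simulated, and the range needs large linear slopes that the documents do not give.
- *That early termination makes the loss worse.* In points it is generally smaller, because both tests weaken. What grows is the chance of missing a modifier with either test.
- *That the three H-score bands waste 4 interaction df against 2.* SAP 2.4.5.1.2 allows small subgroups to be pooled. With about 1% of patients in the low band, roughly one in 120, all 4 df could rarely be estimated.
- *That this is the only analysis of tumour biology.* SAP 2.4.5.2 plans a model for predictive or prognostic factors, and SAP 2.4.7.2 relates tumour and cell-free DNA findings to Ki67 change.
- *That the stepwise models use the bands.* They refer to the Table 4 factors without stating the coding.

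**Conclusion.** The point holds as a modest improvement to an exploratory analysis. The interaction tests rest on bands alone, measured values exist for at least four of the five factors, and for Ki67 the continuous term is already in the model. At 40 per arm, banding costs about 10 to 25 points of power for Ki67, age and H-score, provided that the modifier is roughly linear, worth 0.35 to 0.693 log units per SD, and distributed as assumed above. For a weak modifier the cost is negligible, and for a step at the cut it reverses. No primary or secondary estimate changes.

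**What to change.** In SAP 2.4.5.1.2:
- Keep the Table 4 bands for the per-subgroup geometric LS-means and ratios.
- Base the interaction p-value on the measured scale: age, ER H-score, log tumour size, and PgR if it is stored as a number.
- For baseline Ki67, add treatment-by-log(Ki67pre) to the primary ANCOVA and omit the 20% indicator.
- Keep race and tumour stage categorical.
- State the same continuous coding for the stepwise linear model here and the stepwise logistic model in SAP 2.4.5.2.
- Check linearity with a non-linear term and against the reported band estimates, and plot the fitted treatment effect against each factor.
- State which PgR measure lies behind the 20% cut.

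The cost is a few sentences in the SAP and a small programming change, with no new data. The downside is the linearity assumption, which the check above addresses.
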